## **7.7 CONCOMITANT MEDICINES**

A complete list of drugs that are conditionally allowed and drugs that are not allowed as concomitant medicines for either episodic or chronic use or as Rescue Medicine is provided in [Appendix 2](#). During the Pretreatment, Treatment, and RW Periods, patients may use dispensed, protocol-permitted laxatives (bisacodyl tablets or suppositories) as Rescue Medicine when at least 72 hours have passed since their previous BM or when their symptoms become intolerable. In order to qualify for randomization into the Treatment Period, patients must not have used Rescue Medicine on the day before the Randomization Visit or on the day of the Randomization Visit prior to randomization. Patients must agree to refrain from using Rescue Medicine from the time they arrive at the clinic for the Randomization Visit through the day after randomization.

At the Screening Visit, all ongoing medicines or investigational products taken by the patient will be recorded. Past use of certain medications to manage IBS-C symptoms, even if not ongoing at the time of the Screening Visit, will be recorded in the Prior IBS-C Symptom Management Assessment (refer to Section [8.2.6](#) and [Appendix 7](#)) at the Screening Visit.

Any over-the-counter or prescription laxatives, suppositories, or enemas used to treat IBS-C may not be used during the Pretreatment, Treatment, and RW Periods and may not be used on the day before the Pretreatment Visit. Other prohibited medicines may not be used during the Pretreatment, Treatment, and RW Periods and may not be used during the 14 days before the Pretreatment Visit (refer to [Appendix 2](#)). Thereafter, any changes in concomitant medicines or new medicines added will be recorded on the eCRF. Concomitant medicines will be recorded at study visits throughout the entire trial. Rescue Medicine use will be documented by the patient via eDiary.

## **7.8 TREATMENT COMPLIANCE**

Study drug will be administered to the patient by study center staff at the Randomization Visit. For all other days in the Treatment Period and RW Period, study drug will be taken by the patient once daily in the morning at least 30 minutes before breakfast. Study drug accountability will be closely monitored during the Treatment Period and RW Period by counting the number of capsules returned and recording that information on the eCRF. Every effort will be made to collect all unused study drug. Additionally, patients will be asked about the number of capsules lost and that information will be recorded on the eCRF.

## **8. STUDY PROCEDURES AND ASSESSMENTS**

### **8.1 EFFICACY ASSESSMENTS**

#### **8.1.1 Primary Efficacy Assessments**

The efficacy assessments that will be used to determine the primary efficacy endpoint (Section 10.4.1) are the daily patient assessments of abdominal pain, abdominal discomfort, and abdominal bloating at their worst (ie, the components of the abdominal score).

##### ***Daily Patient Assessment of Abdominal Pain at its Worst***

Patient assessment of abdominal pain at its worst will be collected via a daily evening report in the eDiary. The rating of abdominal pain at its worst during the previous 24 hours on an 11-point NRS will be provided by the patient answering the following question:

“How would you rate your worst abdominal pain in the past 24 hours?”

*<eDiary presents NRS where 0 is anchored with “No abdominal pain” and 10 is anchored with “Worst possible abdominal pain”>*

##### ***Daily Patient Assessment of Abdominal Discomfort at its Worst***

Patient assessment of abdominal discomfort at its worst will be collected via a daily evening report in the eDiary. The rating of abdominal discomfort at its worst during the previous 24 hours on an 11-point NRS will be provided by the patient answering the following question:

“How would you rate your worst abdominal discomfort in the past 24 hours?”

*<eDiary presents NRS where 0 is anchored with “No abdominal discomfort” and 10 is anchored with “Worst possible abdominal discomfort”>*

##### ***Daily Patient Assessment of Abdominal Bloating at its Worst***

Patient assessment of abdominal bloating at its worst will be collected via a daily evening report in the eDiary. The rating of abdominal bloating at its worst during the previous 24 hours on an 11-point NRS will be provided by the patient answering the following question:

“How would you rate your worst abdominal bloating in the past 24 hours?”

*<eDiary presents NRS where 0 is anchored with “No abdominal bloating” and 10 is anchored with “Worst possible abdominal bloating”>*

### **8.1.2 Secondary Efficacy Assessments**

The efficacy assessments that will be used to determine the secondary efficacy endpoints are the daily patient assessments of abdominal pain, abdominal discomfort, and abdominal bloating at their worst, as described in Section 8.1.1.

### **8.1.3 Additional Efficacy Assessments**

In addition to the primary/secondary efficacy assessments, the following efficacy assessments are used in determining the additional efficacy endpoints.

#### ***Complete Spontaneous Bowel Movement***

The CSBM assessment is based on the eDiary questions that determine whether a BM is a CSBM:

- **BM Day and Time**  
Patients will report BMs on an event-driven basis. An evening report will ask whether the patient entered all BMs for that day, and collect BMs not previously entered for that day.
- **Association with a Sense of Complete Evacuation**  
This is assessed by the patient answering the following eDiary question for each BM:  
“Did you feel like you completely emptied your bowels after your bowel movement?”

1=Yes

2=No

- **Day of Any Laxative Use**  
Patients will report use of bisacodyl or other laxatives, suppositories, or enemas on an event-driven basis. An evening report will ask whether the patient entered all laxative use for that day, and collect bisacodyl or other laxatives, suppositories, or enemas not previously entered for that day.

Each day of the Pretreatment, Treatment, and RW Periods, the patient will complete eDiary entries on an event-driven basis to report BMs, and whether the BM was associated with a sense of complete evacuation. (The patient is also asked to provide assessments of stool consistency and straining, which are described below.) The patient will also complete eDiary entries on an event-driven basis to report use of protocol-permitted bisacodyl (tablets or suppositories) or other laxatives, suppositories, or enemas to treat their symptoms. Patients will complete a daily evening report to enter any BMs and laxative usage not previously reported by the patient for that day (recall is limited to 24 hours or to the time of the previous evening's report).

### ***Spontaneous Bowel Movement***

The SBM assessment is based on the eDiary questions (described above) that determine whether a BM is an SBM:

- BM day and time
- Day of Any Laxative Use

### ***Stool Consistency (BSFS)***

Patient assessment of stool consistency will be collected using two questions by eDiary entry on an event-driven basis (ie, for each BM reported in the eDiary).

For each BM, the patient assesses his/her stool using the BSFS ([Appendix 4](#)) which depicts the stool consistency characteristics along with descriptions for each of them. The patient assigns a corresponding score for each BM. The BSFS is a well-accepted and widely-used measurement of stool consistency.[\(14\)](#) The 7-point ordinal BSFS is provided below (see [Appendix 4](#) for full scale including pictures):

“Please describe the form of your stool using the following scale where:”

- 1=Separate hard lumps like nuts (difficult to pass)
- 2=Like a sausage but lumpy
- 3=Like a sausage but with cracks on the surface
- 4=Like a sausage or snake, smooth and soft

- 5=Soft pieces with clear-cut edges (easy to pass)
- 6=Fluffy pieces with ragged edges, a mushy stool
- 7=Watery, no solid pieces (entirely liquid)

The patient also assesses his/her stool using a 5-point ordinal scale described below.

### ***Straining***

Patient assessment of straining will be collected by eDiary entry on an event-driven basis (ie, for each BM reported in the eDiary). For each BM, degree of straining will be assessed by the patient using the following 5-point ordinal scale:

“How much did you strain during your bowel movement?”

- 1=Not at all
- 2=A little (mild straining)
- 3=A fair amount (moderate straining)
- 4=A large amount (severe straining)
- 5=An extreme amount (extremely severe straining)

### ***Stool Consistency (5-point ordinal scale)***

In addition to the patient assessment of stool consistency using the BSFS (described above), patients will also assess stool consistency by daily eDiary entry on an event-driven basis using a 5-point ordinal scale:

“How would you describe the consistency of your stool?”

- 1=Very hard
- 2=Hard
- 3=Neither too hard nor too soft
- 4=Loose but not watery
- 5=Very loose and watery

### ***Weekly Patient Assessment of Constipation Severity***

Patient assessment of constipation severity will be reported weekly by eDiary entry. The rating of constipation severity during the previous 7 days on a 5-point ordinal scale will be provided by the patient answering the following question:

“On average, how would you rate your constipation during the past 7 days?”

1=None

2=Mild

3=Moderate

4=Severe

5=Very severe

### ***Weekly Patient Assessment of IBS Symptom Severity***

Patient assessment of IBS symptom severity will be reported weekly by eDiary entry. The rating of IBS symptom severity during the previous 7 days on a 5-point ordinal scale will be provided by the patient answering the following question:

“On average, how would you rate your IBS symptoms during the past 7 days?”

1=None

2=Mild

3=Moderate

4=Severe

5=Very severe

### ***Weekly Patient Assessment of Adequate Relief***

Patient assessment of adequate relief of IBS symptoms will be reported weekly by eDiary entry. The rating of adequate relief during the previous 7 days on a binary scale will be provided by the patient answering the following question:

“Overall, have you had adequate relief from your IBS symptoms during the past 7 days?”

1=Yes

2=No

### ***Weekly Patient Assessment of Treatment Satisfaction***

Patient assessment of treatment satisfaction will be reported weekly by eDiary entry each week after the Randomization Visit. Patients will answer the following question on a 5-point ordinal scale:

“Overall, how satisfied are you with the study medication’s ability to relieve your IBS symptoms?”

1=Not at all satisfied

2=A little satisfied

3=Moderately satisfied

4=Quite satisfied

5=Very satisfied

## **8.1.4                   Health Economics and Outcomes Research Assessments**

### ***IBS-QOL***

The IBS-QOL is an instrument for assessing the impact of IBS on a patient's quality of life ([Appendix 5](#)). The IBS-QOL will be completed at the Randomization Visit prior to the patient receiving study drug and at subsequent visits as specified in the [Schedule of Evaluations](#). At each of the designated visits, the assessment will be triggered by site personnel on the patient's eDiary for the questionnaire to be self-administered by the patient.

### ***CDC Healthy Days Core Module (CDC HRQOL-4)***

The CDC Healthy Days Core Module (CDC HRQOL-4; [Appendix 6](#)) assesses a person's perceived health status through 4 questions that assess self-rated health, numbers of recent days when physical health or mental health was not good, and number of recent days with limitations due to poor physical or mental health. For the CDC HRQOL-4 items, recent is defined as during the past 30 days. The CDC HRQOL-4 will be completed at the Randomization Visit prior to the patient receiving study drug and at subsequent visits as specified in the [Schedule of Evaluations](#). At each of the designated visits, the assessment will be triggered by site personnel on the patient's eDiary for the questionnaire to be self-administered by the patient.

## **8.1.5                   Completion of eDiary Assessments**

To ensure patient compliance with the completion of the evening eDiary report, alarms occurring at 8, 9, 10, and 11 PM will be programmed to alert the patient that he/she has not completed the evening eDiary report. Upon completion of the evening eDiary report, the alarm will no longer be active for the remainder of that day. If the patient does not complete the evening report prior to midnight, that day's evening report will no longer be available for reporting by the patient and all evening assessments for that day will be considered missing.

Patient compliance with the daily eDiary completion requirement will be verified by site staff as specified in the [Schedule of Evaluations](#).

## **8.2 SAFETY ASSESSMENTS**

Safety will be evaluated by AE reports (discussed herein), standard clinical laboratory assessments, vital signs, physical examinations, and medical history. Planned timepoints for all safety assessments are provided in the [Schedule of Evaluations](#).

### **8.2.1 Adverse Events**

#### **8.2.1.1 Definitions**

##### Adverse Event

An AE is any untoward medical occurrence associated with the use of a drug in humans, whether or not considered drug-related.

An AE, therefore, can be any unfavorable and unintended sign (including an abnormal laboratory finding, for example), symptom, or disease temporally associated with the use of a medicinal product, whether or not considered related to the medicinal product.

**Note:** A procedure is not an AE, but the reason for a procedure may be an AE.

##### Serious Adverse Event

An AE is considered “serious” if, in the view of either the investigator or Sponsor, it results in any of the following outcomes:

- Death
- Life-threatening experience: An AE is considered "life-threatening" if, in the view of either the investigator or Sponsor, its occurrence places the patient or subject at immediate risk of death. It does not include an AE that, had it occurred in a more severe form, might have caused death.
- Inpatient hospitalization or prolongation of an existing hospitalization: AEs requiring hospital admissions that are less than 24 hours in duration do not meet this criterion. A scheduled hospitalization for a preexisting condition that has not worsened during participation in the trial does not meet this criterion. Preplanned hospitalizations for an elective medical/surgical procedure or routine check-ups do not meet this criterion.

- Persistent or significant disability or incapacity or substantial disruption of the ability to conduct normal life functions
- A congenital anomaly or birth defect
- Is considered to be an important medical event: Important medical events that may not result in death, be life-threatening, or require hospitalization may be considered serious when, based upon appropriate medical judgment, they may jeopardize the patient and may require medical or surgical intervention to prevent one of the outcomes listed in this definition. Examples of such medical events include allergic bronchospasm requiring intensive treatment in an emergency room or at home, blood dyscrasias or convulsions that do not result in inpatient hospitalization, or the development of drug dependency or drug abuse.

### Treatment-emergent Adverse Event

A treatment-emergent AE (TEAE) is an event that emerges, or a preexisting event that worsens, any time after administration of the first dose of study drug (Day 1).

#### **8.2.1.2 Classification of an Adverse Event**

##### **8.2.1.2.1 Severity**

The investigator or delegated physician will provide an assessment of the severity of each AE by recording a severity rating in the patient's source documentation and on the AE page of the patient's eCRF. *Severity*, which is a description of the intensity of manifestation of the AE, is distinct from *seriousness*, which implies a patient outcome or AE-required treatment measure associated with a threat to life or functionality. Severity will be assessed according to the following scale:

**Mild:** A type of AE that is usually transient and may require only minimal treatment or therapeutic intervention. The event does not generally interfere with usual activities of daily living.

**Moderate:** A type of AE that is usually alleviated with additional specific therapeutic intervention. The event interferes with usual activities of daily living, causing discomfort, but poses no significant or permanent risk of harm to the research participant.

**Severe:** A type of AE that interrupts usual activities of daily living, or significantly affects clinical status, or may require intensive therapeutic intervention.

AEs should be recorded using the maximum intensity of the event (eg, if a subject reported nausea lasting 3 days, one start date and stop date should be recorded along with the maximum intensity experienced for that event over that 3-day timeframe).

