### **8.2.1.3 Procedures for Recording Adverse Events**

The investigator will record all AEs from the time informed consent is obtained until completion of trial participation (eg, early termination or Week 16/EOT Visit). At each trial visit, the investigator will inquire about the occurrence of AEs/SAEs since the last visit.

The occurrence of an AE or SAE may come to the attention of trial center personnel during trial visits and interviews of a trial patient presenting for medical care, or upon review by a site monitor. All AEs including SAEs will be captured on the appropriate eCRF. Information to be collected includes event description, time of onset, clinician's assessment of severity, relationship to study drug (assessed only by those with the training and authority to make a diagnosis), and time of resolution/stabilization of the event. All AEs occurring while on study must be documented appropriately regardless of relationship. All AEs will be followed to adequate resolution or stabilization.

Any medical condition that is present at the time that the patient is screened and does not deteriorate (worsen in severity and/or frequency) should be recorded as Medical History and not as an AE. However, if the patient's condition deteriorates at any time during the trial, it will be recorded as an AE. AEs characterized as intermittent require documentation of onset and duration of each episode.

Pretreatment AEs will be collected and captured in the patient's source documentation from the time the patient signs the ICF until the patient receives study drug. Pretreatment AEs in randomized patients will additionally be entered on the AE page of the patient's eCRF.

Laboratory abnormalities, changes in vital signs, and physical examination findings should be considered AEs and reported on the AE page of the patient's eCRF only if the investigator considers them clinically significant and/or they necessitate intervention.

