### **10.6.1               Adverse Events**

Adverse Event Verbatim Terms will be coded in the EDC system against the most current version of MedDRA available at the start of the trial (or newer).

An AE that occurs during the Treatment Period will be considered a treatment-emergent AE (TEAE) for the Treatment Period if it was not present prior to the date of the first dose of double-

blind study drug, or was present prior to the date of the first dose but increased in severity during the Treatment Period.

Similarly, an AE that occurs on or after the date of the first dose of double-blind study drug for the RW Period (up to 1 day after the last dose of double-blind study drug) will be considered a TEAE for the RW Period if it was not present prior to the date of first dose of study drug for the Treatment Period, or was present prior to the date of the first dose for the Treatment Period but increased in severity on or after the date of the first dose for the RW Period.

An AE that occurs on or after the date of the first day of dosing in the RW Period (up to 1 day after the last dose of double-blind study drug) will be considered a newly-emergent adverse event (NEAE) for the RW Period if it was not present prior to the date of the first calendar day of dosing in the RW Period, or was present prior to the date of the first calendar day of dosing in the RW Period, but increased in severity on or after the date of the first calendar day of dosing in the RW Period.

If more than one AE is reported prior to the first dose of double-blind study drug and coded to the same preferred term, the AE with the greatest severity will be used as the benchmark for comparison with the AEs occurring during the Treatment and RW Periods that were also coded to that preferred term. An AE that occurs more than 1 day after the last dose of double-blind study drug will not be counted as a TEAE or NEAE.

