#### **7.11.1            *Adverse Events***

Adverse events will be coded by system organ class and preferred term using the MedDRA dictionary, version 21.0.

An AE that occurs during the Treatment Period will be considered a treatment-emergent adverse event (TEAE) if it was not present prior to the date of the first dose of double-blind study drug or was present prior to the date of the first dose but increased in severity during the Treatment Period. If more than 1 AE was reported before the first dose of double-blind study drug and coded to the same preferred term, the AE with the greatest severity will be used as the benchmark for comparison with the AEs occurring during the Treatment Period that were also coded to that preferred term.

An AE that occurs on or after the date of the first dose of the double-blind study drug for the RW Period will be considered a TEAE for the RW Period (RW TEAE) if it was not present prior to the date of the first dose of double-blind study drug of the Treatment Period or was present prior to the date of the first dose of double-blind study drug for the Treatment Period but increased in severity on or after the date of the first dose of the double-blind study drug for the RW Period. An AE that occurs more than 1 day after the last dose of study drug in the RW Period will not be considered a RW TEAE.

An AE that occurs on or after the date of the first dose of the double-blind study drug for the RW Period will be considered a newly emergent adverse event (NEAE) for the RW Period if it was not present prior to the date of the first dose of the double-blind study drug for the RW Period or was present prior but increased in severity after receiving RW period double-blind study drug. An AE that occurs more than 1 day after the last dose of double-blind study drug will not be counted as an NEAE.

The period in which a serious adverse event (SAE) occurred will follow the methods defined above for TEAEs, RW TEAEs, and NEAEs. [Table 7.11-1](#) summarizes the classification of AEs.

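### For a continuous AE that spans the first dose or RW Day 1, the protocol's record holds one maximum intensity and no date of worsening, so the severity-increase parts of TEAE, RW TEAE and NEAE cannot be derived

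*Protocol*

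**What the plan says.** **Recording.** Protocol 8.2.1.2.1 gives a general instruction: "AEs should be recorded using the maximum intensity of the event". Its illustration is nausea lasting three days, for which "one start date and stop date should be recorded along with the maximum intensity experienced for that event over that 3-day timeframe". Protocol 8.2.1.3 then lists what is captured: "Information to be collected includes event description, time of onset, clinician's assessment of severity, relationship to study drug", and the time of resolution or stabilization. No item dates a change in severity, and neither document tells sites to open a new record when an ongoing AE worsens.

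**Classification.** Each emergence definition has a part for AEs that are already present:

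- TEAE: Protocol 8.2.1.1 includes "a preexisting event that worsens, any time after administration of the first dose of study drug (Day 1"). Protocol 10.6.1 words it for analysis as an AE that "was present prior to the date of the first dose but increased in severity during the Treatment Period".
- RW TEAE: SAP 7.11.1 includes an AE that predates the first Treatment Period dose if it "increased in severity on or after the date of the first dose of the double-blind study drug for the RW Period".
- NEAE: SAP 7.11.1 includes an AE that "was present prior but increased in severity after receiving RW period double-blind study drug".

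**Benchmark.** Where several pre-dose AEs share a preferred term, Protocol 10.6.1 says "the AE with the greatest severity will be used as the benchmark for comparison with the AEs occurring during the Treatment and RW Periods". SAP 7.11.1 has the same rule for the Treatment Period.

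**The concern.** Each severity-increase part compares intensity before a dated boundary with intensity after it. A record holding one onset date and one maximum cannot supply that comparison.

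The stakes are largest at RW Day 1, when every placebo completer moves to linaclotide and linaclotide completers are rerandomized 1:1. The NEAE is the category that isolates AEs arising or worsening after that switch. Take a Placebo-290 patient with mild nausea from Week 11 that becomes severe on RW Day 3. The described record shows severe nausea with a Treatment Period onset. It would be tabulated as a severe TEAE on placebo and would not be an NEAE, although the severe phase occurred on linaclotide.

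SAP 7.11.1 assigns the period of a serious AE by the same definitions, so the gap reaches those tables too.

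**Working it through.** The plan states no figure to reproduce here. The check applies the definitions in Protocol 10.6.1, SAP 7.11.1 and SAP Table 7.11-1 to seven severity paths of one continuous AE. This is done once with dated severities and once with a single record (onset date plus overall maximum). With the single record, start date is the only usable information.

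| Path of one continuous AE | With dated severity | From the single record |
|---|---|---|
| 1. New onset in Treatment | TEAE | Same |
| 2. New onset in RW | RW TEAE and NEAE | Same |
| 3. Pre-dose, never worsens | None | Same |
| 4. Treatment onset, stable into RW | TEAE, not NEAE | Same; RW TEAE status turns on the meaning of *occurs* |
| 5. Pre-dose mild, severe in Treatment | TEAE | None |
| 6. Pre-dose mild, severe in RW | RW TEAE and NEAE | None |
| 7. Treatment onset mild, severe in RW | TEAE as mild; RW TEAE and NEAE as severe | TEAE as severe; not NEAE; RW TEAE status turns on the meaning of *occurs* |

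Paths 5, 6 and 7 fail. Treating every spanning AE as worsened would not repair this, because stable AEs (path 3, and path 4 for the NEAE) would then be misclassified.

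**Benchmark side effect.** In path 5 the record carries a pre-dose onset and a severity reached only after dosing. If it serves as the pre-dose benchmark for its preferred term, a later separate moderate episode is compared with severe rather than mild. It then fails to count as a TEAE.

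**Do other clauses cover paths 5 to 7?**

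- Protocol 8.2.1.3, deteriorating conditions: applies to conditions present at screening.
- Protocol 8.2.1.3, intermittent AEs: applies to separate episodes.
- Protocol 8.2.1.2.3: applies to abnormal laboratory values or conditions under treatment at baseline.
- Same-term benchmark: compares separate records and cannot split one.
- SAP 9.7 to 9.9: deal with missing severity, relationship and dates, not with a change in severity.

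None covers a continuous AE that starts after consent and spans a boundary.

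**Where path 7 crosses treatments.** Let *p* and *l* be the placebo and linaclotide patients entering RW. The share who switch drug is (*p* + *l*/2)/(*p* + *l*).

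- No dropout: (300 + 150)/600 = 450/600 = 75%.
- Equal dropout of 10% (assumed): 405/540 = 75%.
- Equal dropout of 30% (assumed): 315/420 = 75%.
- Unequal entry, 90% of placebo and 80% of linaclotide (assumed): (270 + 120)/510 = 76%.
- The reverse: (240 + 135)/510 = 74%.

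For the remaining quarter or so (linaclotide throughout), path 7 puts the severity in the wrong period but under the right drug.

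**The case against.** **The single pair of dates is only an example.** It concerns three-day nausea and does not forbid a new record at a boundary. This stands. The sentence before it, however, is a general instruction to use the maximum intensity of the event, and that alone removes the before-and-after comparison.

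**The field list is not exhaustive, and the eCRF guidance is not in the documents.** This also stands. SAP 9.9 shows that the AE form identifies a trial period, which is not in the 8.2.1.3 list. Completion instructions might already require a new record on worsening. The point is therefore limited to the record that the protocol describes; neither document points to a remedy elsewhere.

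**The benchmark rule presupposes separate records.** It would work if worsening opened one, but nothing says that it does.

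**The Week 11 nausea case may still be an RW TEAE.** Correct. The RW TEAE reference period is Screening and Pretreatment only. If an AE ongoing in RW is held to occur there, it qualifies without any dated worsening. The NEAE is lost on either reading.

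**Rebound is measured elsewhere.** A reader might infer that the trial could not detect rebound. The documents do not support that. Protocol 5.2 describes rebound as symptoms worsening relative to baseline, and the daily eDiary endpoints summarized by sequence in RW measure abdominal and bowel symptoms directly, without AE records.

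**The consequence is limited.** Safety is descriptive (Protocol 10.6), and patients with serious AEs or AEs leading to discontinuation are listed individually. No hypothesis test is affected.

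**Conclusion.** The point holds for one class of event: a continuous AE that starts after consent and spans the first dose or RW Day 1. For that class the described record cannot support the severity-increase parts of the three definitions.

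- **Worsening in Treatment of a pre-dose AE:** omitted as a TEAE, and able to inflate the benchmark for its preferred term.
- **Worsening in RW of a pre-dose AE:** lost as an RW TEAE and NEAE.
- **Worsening in RW of a Treatment-onset AE:** lost as an NEAE, with its RW severity shown under the Treatment Period.

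Two stronger readings go too far. A reader might infer that worsening AEs in general cannot be classified; deteriorating conditions present at screening and intermittent AEs recorded by episode can be, as can new-onset AEs. A reader might also infer that every such AE is credited to the wrong treatment. Worsening after Day 1 causes omission. Credit to the wrong drug arises only for the severity of Treatment-onset AEs that worsen in RW, among the roughly 75% of entrants who switch, assuming equal dropout.

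The documents give no frequency of spanning AEs or of their worsening, so the number of affected patients cannot be sized. The conclusion assumes that no eCRF instruction outside these documents already dates severity changes. It merits correction, but it does not threaten the efficacy conclusions.

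**What to change.** Amend Protocol 8.2.1.2.1 and 8.2.1.3, and the eCRF completion instructions, so that maximum intensity is recorded within each period. When an AE ongoing at the first dose or first RW dose later increases in severity, sites should enter either a linked new record or a dated severity change.

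In SAP 7.11.1, derive the severity-increase parts of TEAE, RW TEAE and NEAE, and the pre-dose benchmark, from those dated severities. State there whether an AE with Treatment Period onset that is still ongoing in RW counts as occurring in RW.

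Paths 5, 6 and 7 then classify as the plan defines. The cost is a few lines of text and a few extra AE entries per site, with no new visits or tests. If dates of worsening are not captured during conduct, recovering them later means going back to source documents.
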